5.1 Treatments During the Study

5.1.1 Treatment for *EYS*-Related Retinal Degeneration

578 Participants *enrolled into the final study cohort* should not plan to enroll into experimental
 579 treatment trials of underlying conditions related to *EYS* mutations during the 4-year study
 580 duration. Participants who do enroll into such a trial will be evaluated by the FFB Consortium
 581 Executive Committee to determine if they may continue participating in the Pro-*EYS* study.
 582

5.1.2 Treatment for Cystoid Macular Edema

584 Participants *enrolled into the final study cohort* who are receiving treatment for CME
 585 throughout the duration of the study may continue doing so without affecting their participation
 586 in the Pro-*EYS* study.
 587

5.1.3 Intraocular Surgical Procedures

589 Participants *enrolled into the final study cohort* who have intraocular surgery during the course
 590 of the study should have follow-up visits timed either before the surgery date or at least 3 months
 591 after the surgery date. Clinical sites should make reasonable efforts to schedule the participant's
 592 follow-up visit as close to the visit target window as possible.

593

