- Baseline Visit date (defined as the start date of all Baseline testing) must be no later than 2 weeks after receiving confirmation of meeting **final study cohort criteria** from the CGA (and if possible, within 90 days of the Screening Visit date). All Baseline testing must be completed within 7 days of the Baseline Visit date, except PROs as specified
- All Follow up visit testing must be completed on the same day, except PROs as specified
- If ERG has been undetectable in the past, no need to perform at baseline, at investigator's discretion
- If ERG is undetectable at baseline, no need to perform at 48M, at investigator's discretion
- For static perimetry and microperimetry, all Vision Cohort 1 and 2 participants will complete two tests at baseline. The results will be compared according to the **visual field criteria** (section 3.2) to determine if a third test is needed.
- Kinetic VF III4e performed within the last 18 months prior to or including the Screening Visit date for Vision Cohort determination only
- Ophthalmic exam includes slit-lamp biomicroscopy, indirect ophthalmoscopy and intraocular pressure (IOP). IOP measurements will be taken prior to pupil dilation. Whenever possible the site should make its best effort to ensure that the exam takes place at approximately the same time of the day at each visit and with the same equipment
- PROs will be completed by participants who agree to answer these additional questions; may be completed in person or remotely any time within 6 months after Baseline or +/- 6 weeks of 24 or 48-month follow-up visits
- If the Baseline visit date is more than 90 days after the Screening Visit date, all Visual acuity procedures must also be completed

Visit Schedule for Vision Cohort 3

Visit	Screening	Baseline	12M	24M	36M	48M
Visit Target Windows	(up to Day -90) ^a	(Day 0) ^b	Wk 52 ± 4 (Phone call only)	Wk 104 ± 4 (Phone call only)	Wk 156 ± 4 (Phone call only)	Wk 208 ± 4 ^c
Participant-Level Procedures						
Informed Consent	X					
Demographics/Medical History (including pre-existing conditions, patient-reported daily activities and medications)	X					
Physical Exam (including height, weight and blood pressure)		X				
Concomitant Medications/Adverse Events		X	X	X	X	X
Patient Reported Outcomes (ULV-VFQ-50, PROMIS®-29, MRDQ and ViSIO-PRO) ^f		X				X
Ocular Procedures - All testing performed in each eye						
Complete Ophthalmic Exam ^e	X					X

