 162 consent process
- 163 2. Ability to return for all study visits over 48 months
- 164 3. Age \geq 18 years
- 165 4. Must meet one of the Genetic Screening Criteria, defined below:
- 166 • **Screening Group A:** At least 2 disease-causing variants in the *EYS* gene which
 167 are **homozygous** or **heterozygous in trans**, based on a report from a clinically-
 168 certified lab (or a report from a research lab that has been pre-approved by the
 169 Genetics Committee)
 - 170 • **Screening Group B:** Only 1 disease-causing variant in the *EYS* gene, based on
 171 a report from a clinically-certified lab (or a report from a research lab which has
 172 been pre-approved by the Genetics Committee)
 - 173 • **Screening Group C:** At least 2 disease-causing variants in the *EYS* gene which
 174 are **unknown phase**, based on a report from a clinically-certified lab (or a report
 175 from a research lab which has been pre-approved by the Genetics Committee)

176

177 *Note pertaining to all Screening Groups: if a participant has a variant(s) of unknown*
 178 *significance, he/she would still qualify as long as there is at least 1 disease-causing variant(s) on*
 179 *the EYS gene.*

180

181 Participant Exclusion Criteria

182 Participants must not meet any of the following exclusion criteria at the Screening Visit in order
 183 to be eligible to *enroll into the genetic screening phase*.

- 184 1. Mutations in genes that cause autosomal dominant retinitis pigmentosa (ADRP), X-
185 linked retinitis pigmentosa (RP), or presence of biallelic mutations in autosomal
186 recessive RP/retinal dystrophy genes other than *EYS*
187 2. Expected to enter experimental treatment trial at any time during this study
188 3. History of more than 1 year of cumulative treatment, at any time, with an agent
189 associated with pigmentary retinopathy (including hydroxychloroquine, chloroquine,
190 thioridazine, and deferoxamine)
191

192 **2.3.1.2 Ocular Criteria**

193 Ocular Inclusion Criteria

194 Both eyes must meet all of the following at the Screening Visit in order for a participant to be
195 eligible to ***enroll into the genetic screening phase.***

- 196 1. Clinical diagnosis of retinal dystrophy
197 2. Clear ocular media and adequate pupil dilation to permit good quality photographic
198 imaging
199

200 Ocular Exclusion Criteria

201 If either eye has any of the following at the Screening Visit, the participant is not eligible to

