202 ***enroll into the genetic screening phase.***

- 203 1. Current vitreous hemorrhage
204 2. Current or any history of rhegmatogenous retinal detachment
205 3. Current or any history of (e.g., prior to cataract or refractive surgery) spherical
206 equivalent of the refractive error worse than -8 Diopters of myopia
207 4. History of intraocular surgery (e.g., cataract surgery, vitrectomy, penetrating
208 keratoplasty, or LASIK) within the last 3 months
209 5. Current or any history of confirmed diagnosis of glaucoma (e.g., based on
210 glaucomatous VF changes or nerve changes, or history of glaucoma filtering surgery)
211 6. Current or any history of retinal vascular occlusion or proliferative diabetic
212 retinopathy
213 7. History or current evidence of ocular disease that, in the opinion of the investigator,
214 may confound assessment of visual function
215 8. History or evidence of active treatment for retinitis pigmentosa that could affect the
216 progression of retinal degeneration, including:
217 a. Any use of ocular stem cell or gene therapy
218 b. Any treatment with ocriplasmin
219 c. Treatment with an ophthalmic oligonucleotide within the last 9 months (last
220 treatment date is less than 9 months prior to Screening Visit date)
221 d. Treatment with any other product within five times the expected half-life of
222 the product (time from last treatment date to Screening Visit date is at least 5
223 times the half-life of the given product)
224

225 **2.3.2 Screening Data Collection and Testing**

226 The study design schematic at the beginning of the protocol shows the flow of the Screening
 227 Visit. The following procedures will be performed at the Screening Visit. The testing
 228 procedures are detailed in the Pro-EYS Procedures Manuals. An overview of the equipment and
 229 technician requirements for all testing is in section 3.4. All ocular testing will be performed in
 230 each eye, right eye (OD) first and then left eye (OS).

231 Participants meeting criteria to continue will be *enrolled into the genetic screening phase*
 232 (section 2.4). Otherwise, the participant will be an *initial screen failure* (section 2.3.3). The
 233 below information will be collected at the Screening Visit:

- 234 1. Contact information (retained at the clinical site and not entered into study database)
- 235 2. Inclusion and exclusion criteria assessment (criteria in sections 2.3.1.1 and 2.3.1.2)
- 236 3. Demographics (including sex, race, ethnicity)

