3.1 Baseline Visit

339 Participants meeting criteria to enter the natural history study (section 2.5) will return for a
 340 Baseline Visit date within 90 days of the Screening Visit date if possible, and no later than 2
 341 weeks after receiving confirmation of meeting *final study cohort criteria* from the CGA. The
 342 Baseline Visit date is the date on which the Baseline Visit testing procedures begin. All Baseline
 343 Visit testing procedures should be completed within 7 days of the Baseline Visit date, except
 344 PROs as specified below.
 345

346 The testing performed at the Screening Visit will serve as baseline measures for the study and
 347 will not be completed again at the Baseline Visit. The only exception is if Baseline Visit date is
 348 more than 90 days after Screening Visit date, then visual acuity testing will be repeated
 349 (including refraction, ETDRS, LLVA if needed, BRVT if needed).
 350

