 390 between the two tests is ≤ 0.5 dB, then the participant passes microperimetry
 391 reliability criteria and a third test is not needed
 - 392 ○ If the absolute value of the difference between the two tests divided by the
 393 average between them is $> 50\%$ AND the absolute value of the difference
 394 between the two tests is > 0.5 dB then the participant does not pass
 395 microperimetry reliability criteria and a third test is needed

396

397 **3.3 Follow-up Visits**

398 The Baseline Visit date is considered study day 0, from which follow-up visit windows are
 399 timed. The Follow-up Visit date will be the date the Follow-up Visit testing procedures started.
 400 All Follow-up Visit testing procedures should be completed on the same date, with the exception
 401 of PROs, which can be completed ± 6 weeks of the required visits as noted below.

402

403 Follow up visits will be conducted at:

Visit	Target	Target Window	Allowable Window
12 Month Visit (Vision Cohorts 1 and 2)	52 Weeks	± 4 Weeks	± 6 Weeks
24 Month Visit (Vision Cohorts 1 and 2)	104 Weeks	± 4 Weeks	± 6 Weeks
36 Month Visit (Vision Cohorts 1 and 2)	156 Weeks	± 4 Weeks	± 6 Weeks
48 Month Visit (All Vision Cohorts)	208 Weeks	± 4 Weeks	± 6 Weeks

404

405 Visits should be scheduled in the target window whenever possible. If circumstances do not
 406 permit this, visits may be scheduled to extend out to the allowable window without being

407 considered a protocol deviation, but the reason for scheduling outside of the target window will
 408 be documented on the visit form. Visits occurring out of the allowable window may still be
 409 completed and used for analysis but will be documented as protocol deviations. Details
 410 regarding when to consider a visit missed are specified in the Pro-EYS Procedures Manuals.

411
 412 The goal will be for all participants to complete all scheduled visits. However, participants who
 413 (because of unforeseen circumstances) are unable or unwilling to return for all follow-up visits
 414 will be permitted to return for key visits only as an alternative to withdrawal from the study. When
 415 a participant is placed into this status, missed visits will not be recorded as protocol deviations
 416 (since they would not be recorded as protocol deviations if the participant was dropped from the
 417 study).

418
 419

420 **3.3.1 Follow-up Visit Testing Procedures**

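### The 3-month interval after intraocular surgery covers Screening and follow-up visits but not Baseline, so an eye operated on between Screening and Baseline can get an early post-operative or mixed baseline.

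*Protocol*

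**What the plan says.** **Screening.** The ocular exclusions in section 2.3.1.2 are judged at one visit: "If either eye has any of the following at the Screening Visit, the participant is not eligible to" enter genetic screening. Exclusion 4 reads "History of intraocular surgery (e.g., cataract surgery, vitrectomy, penetrating" "keratoplasty, or LASIK) within the last 3 months".

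**Follow-up.** Section 5.1.3 says participants in the final study cohort who are operated on in the course "of the study should have follow-up visits timed either before the surgery date or at least 3 months" after it. Section 3.3 lists the follow-up visits as months 12, 24, 36 and 48 and sets Baseline apart from them: "The Baseline Visit date is considered study day 0, from which follow-up visit windows are" timed.

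**Baseline.** The schedule footnotes for all Vision Cohorts say the Baseline date "must be no later than 2 weeks after receiving confirmation of meeting" the final cohort criteria, and, if possible, within 90 days of Screening. They add: "All Baseline testing must be completed within 7 days of the Baseline Visit date, except PROs as specified". Section 3.1 gives the same limits, with "should" for the 7 days. None of these places makes an exception for surgery.

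**Source of baseline values.** Section 3.1 states: "The testing performed at the Screening Visit will serve as baseline measures for the study and" is not done again at Baseline. The one exception is VA testing (refraction, ETDRS, LLVA or BRVT where needed), which is repeated if Baseline is more than 90 days after Screening. The schedule tables put the ophthalmic exam at Screening and not at Baseline. Section 3.2 item 1 has sites record ocular procedures at Baseline, but attaches no action to that record.

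**The concern.** At two of its three kinds of visit, the protocol keeps measurements about 3 months away from intraocular surgery. The third kind, Baseline, has no such interval and is tied to a short deadline set by an unrelated event, the genetic confirmation. Yet Baseline is the reference for the study's main summaries: section 6.2.1 analyses absolute and percent change from baseline, and the risk-factor models adjust for the baseline value.

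For an eye operated on in the gap, two things can go wrong. Its structural and field measures may be taken while the eye is still in the post-operative period that the other two rules avoid. Its VA and lens findings may come from before surgery while everything else comes from after it. Any error in a reference value then carries into every later change score for that eye. VA and lens status are also listed in section 6.2.1 as candidate risk factors, so a stale value misclassifies the eye there too.

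**Working it through.** The protocol gives no figure to reproduce here. The check is a comparison of rules plus date arithmetic.

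**Notation.** Screening is day 0, surgery is day s (s > 0), and Baseline is day b (b > s). Three months is taken as about 91 days (assumption).

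**1. Which rule covers surgery on day s?**
- Exclusion 4 looks back from Screening, so it cannot see s > 0.
- Section 5.1.3 spaces follow-up visits only, and Baseline is not one of them. It is also written for participants already in the final study cohort. Under section 2.4 that status begins when the Central Genetics Auditor (CGA) verifies the criteria, so surgery while genetics are pending comes before it.
- Result: no rule spaces Baseline from surgery on day s.

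**2. Can the site simply wait within the rules?** The longest permitted time from confirmation to the end of Baseline testing is 14 + 7 = 21 days. An eye operated on near confirmation cannot reach about 91 days inside that window.

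**3. Baseline within 90 days of Screening (b ≤ 90), the preferred timing.** The gap is b − s. Since s > 0, b − s < 90. Every eye operated on between the two visits is therefore tested less than 3 months after surgery. VA is not repeated, so the eye's record combines:
- pre-surgery: VA and ophthalmic exam;
- early post-surgery: OCT, autofluorescence and FST and, in Vision Cohorts 1 and 2, static perimetry, microperimetry and contrast sensitivity.

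**4. Baseline more than 90 days after Screening (b > 90).** The gap is still under about 91 days whenever s > b − 91. For example, at b = 120 this holds for any s > 29. VA is now repeated, so it is no longer a pre-surgery value, but it may be an early post-operative one. The ophthalmic exam is still the Screening one.

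**5. Size for one eye (illustration).** Assumptions: 75 letters at Screening; the 5.7% annual VA loss in sections 1.1 and 6.1.4 read as a percentage of letters, which the protocol does not say; a surgical gain of 5, 10 or 15 letters. Annual loss = 0.057 × 75 = 4.3 letters. When the pre-surgery VA is kept as baseline, the gain offsets:

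| Gain (letters) | Years of decline offset in that eye |
|---|---|
| 5 | 5 / 4.3 = 1.2 |
| 10 | 10 / 4.3 = 2.3 |
| 15 | 15 / 4.3 = 3.5 |

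**6. Size for the study mean.** The 90 participants planned for Vision Cohorts 1 and 2 give 90 × 2 = 180 eyes. One eye with a 15-letter gain moves the mean by 15 / 180 = 0.08 letters.

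**The case against.** **The rules do not contradict each other.** A reader might infer a contradiction, but each rule governs a different visit and all can be followed at once. No passage says early post-operative testing is acceptable. This objection stands: the text leaves a gap.

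**The VA problem is conditional.** A reader might infer that every such eye keeps a pre-surgery baseline VA. Section 3.1 does not support that: beyond 90 days VA is repeated. Participants delayed by family testing in Screening Groups B and C are the ones most likely to be covered by that repeat. This stands, though the repeated VA may itself be early post-operative.

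**Such eyes should be uncommon.** Section 1.1 calls posterior subcapsular cataract common in this disease. But ocular inclusion 2 requires both eyes at Screening to have media clear enough for good imaging, and exclusion 7 removes disease that may confound visual function. A cataract that passes these criteria and is then removed within about 3 months should be rare. This stands, and the protocol gives no count.

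**Surgery during follow-up also shifts change scores.** Section 5.1.3 allows it over 48 months, a longer window than this one. True, but there the baseline is sound and the surgery falls between two properly spaced measurements.

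**Safety.** A reader might infer that the gap exposes freshly operated eyes to harm, for instance from the contact-lens ERG electrode. The protocol gives no safety reason for the 3-month interval. Section 5.2.1 describes corneal abrasion as rare and quick to heal, and ERG may be skipped if it was undetectable before. No safety problem is shown.

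**Partly handled already.** Interim procedures are recorded at Baseline, so affected eyes can be identified, and the Procedures Manuals, not at hand, may say more. Recording does not alter section 3.1, which as written still makes the Screening result the baseline. Nor is delay a clean way out: missing the 2-week limit is noncompliance, and so a deviation under section 7.4.

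**Conclusion.** The point holds in a limited form. Followed as written, the protocol can give an eye operated on between Screening and Baseline a reference set taken less than 3 months after surgery. When Baseline is within 90 days of Screening this is certain for every such eye, and the baseline VA is then the pre-surgery value. After 90 days it depends on the surgery date. The ophthalmic exam is out of date in both cases. Only surgery in this interval matters, since earlier surgery outside the exclusion is already about 3 months old at Screening.

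For a single eye the distortion can be large: roughly 1 to 3.5 years of decline under the stated assumptions. For the study it is small: about 0.08 letters on the mean for one eye at the top of that range. A reader might infer a material bias in the progression estimates. The documents do not support that, because the number of affected eyes is unknown and probably low. It is worth correcting because the remedy is short and the error falls on the reference value of each affected eye.

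**What to change.** - **Timing.** The sponsor should reconcile exclusion 4 in section 2.3.1.2, section 3.1, the Baseline footnotes of both visit schedules and section 5.1.3, so that the protocol states how surgery between Screening and Baseline affects the timing of Baseline testing. The interval, and which rule prevails where they compete, are for the sponsor to decide.
- **Baseline values.** In section 3.1 and the schedule footnotes, extend the existing repeat-VA exception to any eye with intraocular surgery recorded between Screening and Baseline, whatever the number of days. Update lens status for that eye, and state that its pre-surgery Screening VA is not used as its baseline.

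The second change removes the mix of pre- and post-surgery values. It does not settle whether the repeated VA is too early, which depends on the first. The cost is a few sentences of amended text and, for the few participants affected, a repeated VA test and a lens-status check at a visit they already attend.

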5.2 Risks and Benefits

595

5.2.1 Risks and Discomforts

597 Most examination procedures are considered part of standard care for retinal degenerations. The
 598 procedures have been standardized for consistency across sites and are not part of a therapeutic
 599 experimental protocol. The only risk for being part of the study over and above standard care is
 600 the unlikely chance that sensitive participant information is viewed by someone outside the
 601 research team who is not authorized. However, special efforts are being made to ensure that this
 602 does not happen. Otherwise, there are no known risks or discomforts beyond those involved in
 603 standard clinical care for patients with retinal degeneration involved in participation in this study,
 604 which involves systematically collecting information in a prospective fashion. The sections
 605 below summarize the risks and discomforts that may be involved in the usual care of the patient
 606 during the period of time of prospective data collection.

- 607 • Risks associated with testing VA, KP, SP, Optos or Spectralis FAF, Near infrared
- 608 reflectance photos, and PRO may include boredom and frustration, but no lasting adverse
- 609 effects are associated with these noninvasive tests
- 610 • Dilating eye drops will be used as part of the ophthalmic examination and before the SD-
- 611 OCT, ERG, FST, and MP. Dilating eye drops may sting, cause light-sensitivity, or an

612 allergic reaction. There is a small risk of inducing a narrow-angle glaucoma attack from
 613 the pupil dilation. However, all participants will have had prior pupil dilation usually on
 614 multiple occasions and therefore the risk is extremely small. If glaucoma occurs,
 615 treatment is available

- 616 • IOP Examination and ERG: In rare instances, the cornea may be scratched during
 617 measurement of intra-ocular pressure or use of a contact lens electrode. An abrasion like
 618 this may be painful, but it heals quickly with no lasting effects. In the event that a
 619 participant experiences a corneal abrasion, a tear ointment may be administered, and an
 620 eye patch or gauze may be placed over the eye
- 621 • The risks of genetic testing include emotional and psychological stress when patients may
 622 learn they have a genetic disease that could be passed along to their children, if
 623 information relating to the family, such as adoption and paternity, could be determined
 624 from these tests. All genetic testing information will be kept in confidential laboratory
 625 documents and medical records. If data gathered through genetic testing is accidentally
 626 released or stolen, it is possible that the information could become available to an insurer,
 627 an employer, a relative, or someone else. There are discrimination protections in US
 628 Federal Law and many State laws, however there is still a small chance that participants
 629 could be harmed if a release occurred

630

631 **5.2.2 Benefits**

632 Study participants are not expected to benefit directly from participation in this study. Subjects
 633 participating in this study may benefit from close attention from the study personnel and PI.
 634 The risks of participating in the study are outweighed by the benefits including increased
 635 attention from the study personnel and the ability to contribute to increased understanding of the
 636 natural history of *EYS*-related retinal degeneration and contribute to future development of
 637 treatments.

638 **5.3 Collection of Pre-Existing Conditions and Medications**

639 *Pre-Existing Condition:* Any medical condition that is either present at screening, a chronic
 640 disease, or a prior condition that could impact the participant's health during the course of the
 641 study (e.g., prior myocardial infarction or stroke) should be recorded.

642 *Medications:* All medication for the treatment of chronic pre-existing conditions, medical
 643 conditions, and/or AEs that the participant is currently taking at screening and during the course
 644 of the study should be recorded. Nutraceuticals and preventative treatment also should be
 645 recorded.

646 **5.4 Participant Compensation**

647 Participant compensation will be specified in the ICF.

648 **5.5 Participant Withdrawal**

649 Participation in the study is voluntary, and a participant may withdraw at any time. For
 650 participants who withdraw, their data will be used up until the time of withdrawal.

651 **5.6 Confidentiality**

652 For security and confidentiality purposes, participants will be assigned an identifier that will be
653 used instead of their name. Protected health information gathered for this study will be shared
654 with the FFB Consortium CC, the Jaeb Center for Health Research in Tampa, Florida, USA. De-
655 identified participant information may also be provided to research sites involved in the study.

656

Chapter 6: Statistical Considerations

657 The approach to sample size and statistical analyses are summarized below. A detailed statistical
 658 analysis plan will be written and finalized prior to the completion of the study. The analysis plan
 659 synopsis in this chapter contains the framework of the anticipated final analysis plan.

660 6.1 Sample Size

661 The sample size evaluation focuses on objective 1 of the study, to characterize the natural history
 662 of retinal degeneration associated with biallelic pathogenic mutations in the *EYS* gene over 4
 663 years on both the structural and functional outcomes of interest. Calculations to address
 664 objective 3, evaluation of possible risk factors associated with progression, are summarized. A
 665 justification of the selected sample size using percent change for the outcomes of interest is
 666 outlined. The precision of the between-eye correlation is also provided.

667 It should be noted that the sample size for Vision Cohort 3 is a convenience sample, i.e., 10
 668 participants. The objectives of including this population are to:

669

- 670 • Establish baseline FST and PRO measurement data in patients with very low vision to be
 671 used in future trials of optogenetics, stem cells and other regenerative technology
- 672 • Establish the most extended range of patients with *EYS* mutations in the measures
 673 possible
- 674 • Obtain cross sectional data in patients with the furthest disease progression
- 675 • Establish which tests are the most useful in patients with the furthest disease progression

676

677 6.1.1 Sample Size Considerations for Evaluating Percent Change from Baseline to 4 Years 678 (All Outcomes)

679 Longitudinal changes on all outcome parameters being collected will be of interest. Change
 680 from baseline to 4 years will be evaluated for sample size purposes. The power/sample size
 681 calculations may be used to consider percent change on any outcome measure from baseline to 4
 682 years.

683 Both eyes of a participant will be assessed for the main outcomes of interest. Thus, if there are N
 684 participants, 2N eyes will be available for analysis. However, outcome measures from 2 eyes of
 685 a person are typically strongly correlated ($r \geq 0.5$). The contribution of information in this case is
 686 $(2/(1+r))$ instead of 2. Values for the multiplier to the number of participants to obtain an
 687 effective sample size are given below:

r	Effective N
0.0	2.00
0.1	1.82
0.2	1.67

0.3	1.54
0.4	1.43
0.5	1.33
0.6	1.25
0.7	1.18
0.8	1.11
0.9	1.05
1.0	1.00

688

689 One objective is to estimate the correlation between eyes for the outcome measures; therefore,
 690 the value of the correlation is not known at the time of study design. We assume here a
 691 correlation of 0.8. This assumption is conservative in that it requires a higher number of
 692 participants than other plausible values of r.

693 The primary way sample size is evaluated is by considering the precision around the point
 694 estimates for the outcome measures of interest. Table 1 (including the table of specific values
 695 corresponding to the graph) provides the half width of the 95% confidence interval (CI) for the
 696 estimated mean percent change for combinations of the standard deviation (SD) of the
 697 distribution of percent change and sample size. The larger the SD, the wider the CI, meaning the
 698 range of possible true values grows.

699

700 **Table 1. Sample size versus half width of 95% confidence interval for the mean percent**
 701 **change for varying standard deviation values**

	Effective Sample Size (N of participants)				
	n=55 (50)	n= 72 (65)	n= 88 (80)	n= 99 (90)	n=110 (100)
SD=20%	5%	5%	4%	4%	4%
SD=30%	8%	7%	6%	6%	6%
SD=40%	11%	9%	8%	8%	7%
SD=50%	13%	12%	10%	10%	9%

702

[figure not shown]
703 **6.1.2 Sample Size Considerations for Comparing Percent Change from Baseline to 4 Years**
 704 **within Subgroups of Interest (All Outcomes)**

705 Another important objective for this natural history study will be to evaluate the association of
 706 possible risk factors with progression of various functional outcome variables (objective 3).
 707 Thus, it will be important to have a large enough total sample size to plan reasonable
 708 comparisons between subgroups. Figure 1 considers various expected SDs and evaluates the

709 power to detect varying differences in average percent change from baseline to 4 years,
 710 comparing subgroups of various equally distributed sizes. If subgroups are not equally sized the
 711 detectable difference (with the same power) will be larger.

712 Note: *within* subgroup point estimates and CIs will also be important. Table 1 above can be
 713 applied to potential subgroup sample sizes as well to consider the precision that would be
 714 observed.

715 **Figure 1. Power to conclude there is a difference given varying true difference values,**
 716 **population standard deviation, and sample size**

717
 718 Power to conclude there is a difference, when true difference in mean percent change is x-axis
 719 value. Assuming various sample size (subgroups close to equal distribution).

720 **6.1.3 Sample Size Considerations for Precision of the Estimate of the Correlation between**
 721 **Eyes**

722 The intraclass correlation coefficient is used to assess the strength of correlation between eyes.
 723 When both eyes have the same mean for the outcome measure, the intraclass correlation
 724 coefficient is equal to the standard Pearson correlation coefficient (r). The distribution of r is not
 725 symmetric; therefore, CIs for the estimated correlation coefficient are not symmetric. A
 726 transformation of r ($z = 0.5 * \ln((1+r)/1-r)$) is used to create a variable that is asymptotically
 727 distributed $N(0, 1/(\sqrt{N-3}))$ under the null hypothesis that $r=0$. The table below provides the
 728 95% CI for different estimates of r from the observed data.

729 **Table 2. 95% Confidence Intervals for an Observed Value of r**

r	N of patients				
	n= 50	n= 65	n= 80	n= 90	n= 100
0.3	(0.02, 0.53)	(0.07, 0.51)	(0.09, 0.49)	(0.10, 0.48)	(0.11, 0.47)
0.4	(0.14, 0.61)	(0.17, 0.59)	(0.20, 0.57)	(0.21, 0.56)	(0.22, 0.55)
0.5	(0.26, 0.68)	(0.29, 0.66)	(0.31, 0.65)	(0.33, 0.64)	(0.34, 0.63)
0.6	(0.39, 0.75)	(0.42, 0.74)	(0.44, 0.72)	(0.45, 0.72)	(0.46, 0.71)
0.7	(0.52, 0.82)	(0.55, 0.81)	(0.57, 0.80)	(0.58, 0.79)	(0.58, 0.79)
0.8	(0.67, 0.88)	(0.69, 0.87)	(0.70, 0.87)	(0.71, 0.86)	(0.72, 0.86)
0.9	(0.83, 0.94)	(0.84, 0.94)	(0.85, 0.93)	(0.85, 0.93)	(0.85, 0.93)

730

731 **6.1.4 Final Sample Size Justification**

732 Longitudinal changes in all outcome parameters being collected will be of interest for objectives
 733 1 and 3. Information on rates of decline for *EYS*, and for inherited retinal degenerations in
 734 general, is very limited.

735 **Data to consider for evaluating sample size:**

- 736 • Valproic Acid Protocol (VPA) Data (a phase II multiple site, randomized, placebo-
 737 controlled trial of oral valproic acid for ADRP) [Placebo group N=44; dataset can be
 738 accessed at this [link](#)]
- 739 ○ Percent Change from Baseline to 1 year, Mean (SD):
- 740 ▪ -0.3% (16%) OD
- 741 ▪ -4.9% (17%) OS
- 742 • Natural history of 15 participants with *EYS* mutations (McGuigan/Jacobson, 2017)
- 743 ○ -5.7% per year for VA [8 participants]
- 744 ○ -5.8% for Inner Segment/Outer Segment (IS/OS) extent
- 745 • Natural history of 12 participants with *EYS* mutations (Miyata/Yoshimura, 2016)
- 746 ○ -5.2 ±3.1% for IS/OS extent

747 **Assumptions made:**

- 748 • Expect average annual decline in *EYS* to be 6.25% per year or 25% by 4 years
- 749 • True SD of percent change at 4 years similar to VPA 1-year SD of around 20%

750 **Based on these assumptions and the impact as presented above, a sample size for the**
 751 **combined Vision Cohorts 1 and 2 of 90 patients or 99 effective eyes has been selected.** With
 752 an effective sample size of 99, the half width of a 95% CI around the point estimate for percent
 753 change would be 4%. A comparison of two equal-sized subgroups would have about 80% power
 754 to conclude there is a difference if the true difference is 11%.

755 Based on the above justification, the total sample size will be 100 participants enrolled.
 756 Recruitment is anticipated to take 10 months from the time of study launch.

757 **6.1.4.1 Synopsis of Justification for All Outcomes**

758 The primary objective of the study is to characterize the natural history of retinal degeneration
 759 using the main outcome measures. Therefore, the precision of these estimates (how tight the CI
 760 is around the point estimate) for all of the outcomes of interest will be of the greatest importance
 761 in the consideration of sample size. With a sample size of 90 participants (effective sample size
 762 N= 99) for Vision Cohorts 1 and 2, all of these outcomes will have 95% CIs no wider than +/-
 763 4% (when analyzed in terms of percent change from baseline) if the SD is within 20%. Based on
 764 the available data, we expect the SD to be within 20%, which would yield CIs no wider than +/-
 765 4%. With an even smaller sample size of 65 participants (effective sample size N= 72), all of
 766 these outcomes will have 95% CIs no wider than +/- 5% if the SD is within 20%. This was
 767 considered acceptable precision to meet our objective for all outcomes of interest.

768 Furthermore, for the additional objective of evaluating risk factors associated with progression of
 769 these outcomes, a sample size of 90 (effective sample size N= 99) participants for Vision Cohorts
 770 1 and 2 will provide enough power to evaluate subgroups, especially those with close to equal
 771 distribution. For example, for 2 subgroups of equal size there will be at least 69% power to
 772 detect differences as small as 10% if SD is within 20%. With a sample size of 65 (effective
 773 sample size N= 72), there will be at least 55% power to detect differences as small as 10% if SD
 774 is within 20%.

775 For objective 4 of evaluating variability and symmetry, a sample size of 90 participants for
 776 Vision Cohorts 1 and 2 will have a 95% CI of (0.34, 0.63) when observed r equals to 0.5, and
 777 (0.72, 0.86) when observed r equals to 0.8. With a smaller sample size of 65 participants, the
 778 95% CI would be (0.30, 0.66) when observed r equals to 0.5, and (0.70, 0.87) when observed r
 779 equals to 0.8. This is considered acceptable precision to meet our objective.

780 **6.2 Data Analysis**

781 The analysis plans below are written with respect to the majority of outcomes of interest.
 782 Analyses will include data on both eyes for each participant, and models and confidence
 783 intervals will adjust for correlation between 2 eyes of the same participant.

784 **6.2.1 Primary Objectives Analyses**

785 The primary objectives of the natural history study and brief analysis plan for each are as
 786 follows.

- 787 1. Characterize the natural history of retinal degeneration associated with biallelic
 788 pathogenic mutations in the *EYS* gene over 4 years, as measured using functional,
 789 structural, and PRO measures
 - 790 a. Analysis plan for functional and structural measures: The distribution of each
 791 outcome at each visit will be summarized (including tabulating categorically, as
 792 well as means, SDs, medians, quartiles, ranges; both the absolute change and
 793 percent change will be evaluated, tests performed multiple times will be analyzed
 794 using average of all available tests). To determine the average annual rate of
 795 progression in the population for each outcome, a repeated measures least squares
 796 regression model will be fit using all available outcome data at baseline and all

797 annual visits. Multiple imputation will be used to impute the outcome values for
 798 all missing time points (including participants who discontinue follow up prior to
 799 48 months). Secondary analyses using binary definitions of outcome measures
 800 will also be explored in time to event analyses; Kaplan-Meier estimates with 95%
 801 confidence intervals will be calculated. Mixed effects linear models for the
 802 continuous outcome measures and for the time-to-event analyses will also be
